# 3.1.1.4. Safety Analysis Set

The **Safety Analysis Set** will include all subjects who (1) are randomized into the study and (2) have received at least 1 dose of blinded randomized study drug. Subjects will be grouped according to the treatment they actually received. This is the primary analysis set for safety analyses.

Adverse event, concomitant medication, pregnancy, and death data collected up to 30 days after permanent discontinuation of the blinded randomized study drug and prior to the first dose date of OL study drug (if applicable) will be included in the safety summaries, unless specified otherwise.

Laboratory data (eg, hematology, chemistry, and urine analysis), vital sign, ECG data collected up to 30 days after permanent discontinuation of the blinded randomized study drug and on or prior to the first dose date of OL study drug (if applicable) will be included in the safety summaries, unless specified otherwise.

## 3.1.2. Analysis Set Used for the All B/F/TAF Analysis

## 3.1.2.1. All B/F/TAF Analysis Set

The **All B/F/TAF Analysis Set** will include all subjects who (1) are randomized into the randomized phase of the study and (2) have received at least 1 dose of the B/F/TAF in the randomized phase or at least 1 dose of the B/F/TAF in the extension phase. This is the primary analysis set for the all B/F/TAF efficacy and safety analyses.

For efficacy analyses, all efficacy data collected for the all B/F/TAF analysis will be included.

For safety analyses, all safety data collected up to 30 days after permanent discontinuation of the last B/F/TAF (including randomized and open label phases) will be included in the safety summaries, unless specified otherwise.

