#### 3.1.1.2. Full Analysis Set

The **Full Analysis Set (FAS)** will include all subjects who (1) are randomized into the study and (2) have received at least 1 dose of blinded randomized study drug. Subjects will be grouped according to the treatment to which they were randomized. For the FAS, all efficacy data collected in the randomized phase, including data collected after the last dose of blinded study drug and on or prior to the first dose date of the OL study drug (if applicable), will be included, unless specified otherwise. This is the primary analysis set for efficacy analyses.

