# 3.2. Subject Grouping

For the randomized phase analyses using the All Randomized Analysis Set or the FAS, subjects will be grouped by the randomized treatment (labeled as B/F/TAF vs. DTG + F/TAF). For all other randomized phase analyses, subjects will be grouped by the actual treatment received. The actual treatment received will differ from the randomized treatment only when the actual treatment received differs from randomized treatment for the entire treatment duration.

For all B/F/TAF analyses, subjects will be grouped into the following 3 groups:

- B/F/TAF group: This group includes all subjects who actually received B/F/TAF in the randomized phase of this study, regardless whether subjects receive any B/F/TAF in the extension phase or not.
- DTG + F/TAF to B/F/TAF group: This group includes all subjects who actually received DTG + F/TAF regimen in the randomized phase of this study and then receive at least 1 dose of B/F/TAF in the extension phase
- All B/F/TAF group: This group includes all subjects who actually received at least 1 dose of B/F/TAF in either phase. This group includes the B/F/TAF group and the DTG + F/TAF to B/F/TAF group. Only data collected on and after the first dose date of B/F/TAF may be included.

Treatment comparisons will only be made between B/F/TAF and DTG + F/TAF for the randomized phase analysis.

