# 3.8.2. Analysis Windows

Subject visits might not occur on protocol specified days. Therefore, for the purpose of analysis, observations will be assigned to two different analysis windows based on the following tables: the analysis windows for the randomized phase analysis are derived relative to the Study Day 1 for the randomized phase analysis, while the analysis windows for the all B/F/TAF analysis are derived relative to the Study Day 1 for the all B/F/TAF analysis.

The analysis windows for HIV-1 RNA, CD4+ cell count, CD4 %, hematology, chemistry, urinalysis, urine pregnancy laboratory tests, eGFRCG, vital signs, and weight are presented in Table 2 and Table 3 for randomized phase analysis and all B/F/TAF analysis separately.

Table 2. Analysis Windows for HIV-1 RNA, CD4+ cell count, CD4 %, HBV DNA, Hematology, Chemistry, Urinalysis, and Urine Pregnancy Laboratory Tests, eGFRCG, Vital Signs, and Weight for Randomized Phase Analysis

Visit ID	Nominal Day	Lower Limit	Upper Limit
Baseline			1
Week 4	28	2	42
Week 8	56	43	70
Week 12	84	71	126
Week 24	168	127	210
Week 36	252	211	294
Week 48	336	295	378
Week 60	420	379	462
Week 72	504	463	546
Week 84	588	547	630
Week K	K*7	(K-6)*7+1	(K+6)*7

Note: Week K is every 12 weeks after previous visit.

Table 3. Analysis Windows for HIV-1 RNA, CD4+ cell count, CD4 %, HBV DNA, Hematology, Chemistry, Urinalysis, and Urine Pregnancy Laboratory Tests, eGFRCG, Vital Signs, and Weight for All B/F/TAF Analysis

	B/F/TAF Group			DTG+F/TAF to 1		
Visit ID	Nominal Day	Lower Limit	Upper Limit	Nominal Day	Lower Limit	Upper Limit
Baseline			1			1
Week 4	28	2	42	NA	NA	NA
Week 8	56	43	70	NA	NA	NA
Week 12	84	71	126	84	2	126
Week 24	168	127	210	168	127	210
Week 36	252	211	294	252	211	294
Week 48	336	295	378	336	295	378
Week 60	420	379	462	420	379	462
Week 72	504	463	546	504	463	546
Week 84	588	547	630	588	547	630
Week 96	672	631	714	672	631	714
Week k	K*7	(K-6)*7+1	(K+6)*7	K*7	(K-6)*7+1	(K+6)*7

NA = Not applicable

Note: For the B/F/TAF group, Study Day 1 is the first dose date of the B/F/TAF received in the randomized phase; For the DTG + F/TAF to B/F/TAF group, Study Day 1 is the first dose date of the B/F/TAF received in the extension phase.

Note: Week K is every 12 weeks after previous visit.

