# 3.8.3. Selection of Data in the Event of Multiple Records in an Analysis Window

Depending on the statistical analysis method, single values are required for each analysis window. For example, change from baseline by visit usually requires a single value, whereas a time to event analysis would not require one value per analysis window. When a single value is needed, the following rule(s) will be used.

If multiple nonmissing numeric observations exist in a window, then records will be chosen as follows:

• For baseline, the latest available record on or prior to the first dose date of study drug for randomized phase analysis or B/F/TAF phase analysis will be selected. If there are multiple records with the same time or no time recorded on the same day, average will be used for the baseline value, except for HIV-1 RNA (see below).

- For postbaseline visits:
  - For CD4+ cell count, CD4%, and HBV DNA, the record(s) collected on the latest day in the window will be selected for analysis.
  - For other numeric observations (ie, except HIV-1 RNA, CD4+ cell count, CD4%, and HBV DNA), the record(s) collected on the day closest to the nominal day for that visit will be selected. If there are 2 days equidistant from the nominal day, the later day will be selected.
  - For any numeric observations except HIV-RNA, if there are multiple records on the selected day, the average will be taken.
- For baseline and postbaseline HIV-1 RNA, the latest (considering both date and time) record(s) in the window will be selected. If both "HIV RNA Taqman 2.0" and "HIV RNA Repeat" (ie, the HIV-1 RNA result obtained from an additional aliquot of the original sample) are available with the same collection time, the results from the "HIV RNA Repeat" will be selected for analysis purposes; otherwise, if there are multiple "HIV RNA Taqman 2.0" records with the same collection time, the geometric mean will be taken for analysis purposes.

If multiple valid nonmissing categorical observations exist in a window, records will be chosen as follows:

- For baseline, the last available nonmissing record on or prior to the first dose date of study drug for randomized phase analysis or B/F/TAF phase analysis will be selected. If there are multiple records with the same time or no time recorded on the same day, the value with the lowest severity will be selected.
- For postbaseline visits, the most conservative value within the window will be selected.

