## 6.1.1.2. US FDA-Defined Snapshot Algorithm

The analysis window at Week 48 is defined as from Study Day 295 to Study Day 378, inclusive. All HIV-1 RNA data collected on-treatment (ie, data collected up to 1 day after permanent discontinuation of study drug) will be used in the US FDA-defined snapshot algorithm. Virologic outcome will be defined as the following categories:

- **HIV-1 RNA < 50 copies/mL:** this includes subjects who have the last available on-treatment HIV-1 RNA < 50 copies/mL in the Week 48 analysis window
- HIV-1 RNA  $\geq$  50 copies/mL: this includes subjects
  - a) Who have the last available on-treatment HIV-1 RNA ≥ 50 copies/mL in the Week 48 analysis window, or
  - b) Who do not have on-treatment HIV-1 RNA data in the Week 48 analysis window and
    - 1) Who discontinue study drug prior to or in the Week 48 analysis window due to lack of efficacy, or
    - 2) Who discontinue study drug prior to or in the Week 48 analysis window due to AE or death and have the last available on-treatment HIV-1 RNA  $\geq$  50 copies/mL, or
    - 3) Who discontinue study drug prior to or in the Week 48 analysis window due to reasons other than AE, death, or lack of efficacy and have the last available on-treatment HIV-1 RNA ≥ 50 copies/mL.
- No Virologic Data in the Week 48 Window: this includes subjects who do not have on-treatment HIV-1 RNA data in the Week 48 analysis window because of the following:
  - a) Discontinuation of study drug prior to or in the Week 48 analysis window due to AE or death and the last available on-treatment HIV-1 RNA < 50 copies/mL, or
  - b) Discontinuation of study drug prior to or in the Week 48 analysis window due to reasons other than AE, death, or lack of efficacy and the last available on-treatment HIV-1 RNA < 50 copies/mL or,
  - c) Missing data during the window but on study drug.

The flowchart of the US FDA-defined snapshot algorithm is provided in Appendix 2.

The Week 48 virologic outcomes for the US FDA-defined snapshot algorithm will be listed.

For switch trials, the US FDA-defined snapshot algorithm classifies subjects who discontinue study drug due to AE or death and have the last available on-treatment HIV-1 RNA value  $\geq 50$  copies/mL in the "HIV-1 RNA  $\geq 50$  copies/mL" category. For treatment naïve study population, these subjects will be classified in the "No Virologic Data in the Week 48 Window" category.

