#### 6.2.2. Analysis of the Efficacy Endpoints for All B/F/TAF Analysis

6.2.2.1. Analysis of the Proportion of Subjects with HIV-1 RNA < 50 copies/mL by Missing = Excluded Approach

The proportion of subjects with HIV-1 RNA < 50 copies/mL will be analyzed using M = E for imputing missing HIV-1 RNA values using the All B/F/TAF Analysis Set for the all B/F/TAF analysis.

• Missing = Excluded (M = E)

In this approach, all missing data will be excluded in the computation of the percentages (ie, missing data points will be excluded from both the numerator and denominator in the computation). The denominator for percentages at a visit is the number of subjects in the All B/F/TAF Analysis Set with non-missing HIV-1 RNA value at that visit.

For M = E analysis, the number and percentage of subjects with HIV-1 RNA in the following categories will be summarized:

- < 50 copies/mL
  - -- < 20 copies/mL
    - < 20 copies/mL Not Detectable

    - < 20 copies/mL Detectable
  - -20 to < 50 copies/mL
- 50 to < 200 copies/mL
- 200 to < 400 copies/mL
- 400 to < 1000 copies/mL
- $\geq 1000 \text{ copies/mL}$

The 95% CI for the proportion of subjects with HIV-1 RNA < 50 copies/mL for a treatment group will be constructed using the Clopper-Pearson exact method. No statistical comparisons will be made for the all B/F/TAF analysis.

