## 6.2.2.2. Analysis of CD4+ Cell Count and CD4%

The analysis of CD4 cell count will be based on on-treatment data (ie, up to 1 day after the last dose date of study drug) using the All B/F/TAF Analysis Set for the all B/F/TAF analysis.

The changes from baseline in CD4+ cell count at each visit will be summarized by treatment group using descriptive statistics. No statistical comparisons will be made for the all B/F/TAF analysis.

Similar analysis will be conducted for CD4% using the All B/F/TAF Analysis Set for the all B/F/TAF analysis.

In addition, the mean and 95% CI of change from baseline in CD4+ cell count over time will be plotted for the all B/F/TAF analysis.

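### The all-B/F/TAF HIV-1 RNA < 50 copies/mL (M=E) table has no on-treatment limit, so samples taken after the last B/F/TAF dose count as B/F/TAF results and can replace the last on-drug value

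*SAP*

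**What the plan says.** **Which data enter.** SAP 3.1.2.1 states: "For efficacy analyses, all efficacy data collected for the all B/F/TAF analysis will be included". The sentence after it gives safety data a 30-day limit; efficacy data get none. SAP 3.2 sets only a start: "Only data collected on and after the first dose date of B/F/TAF may be included". SAP 6.2.2.1 defines the M=E denominator by availability alone: "The denominator for percentages at a visit is the number of subjects in the All B/F/TAF Analysis Set with non-missing HIV-1 RNA value". Item 14 of SAP Appendix 8 adds no on-treatment condition. The on-treatment footnote in SAP Appendix 2 belongs to the Week 48 snapshot flowchart.

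**Which record is used.** SAP 3.8.3: "For baseline and postbaseline HIV-1 RNA, the latest (considering both date and time) record(s) in the window will be selected". SAP 3.8.2 adds that "the analysis windows for the all B/F/TAF analysis are derived relative to the Study Day 1 for the all B/F/TAF analysis".

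**How related data are handled.**
- CD4 in the all-B/F/TAF analysis (SAP 6.2.2.2): "The analysis of CD4 cell count will be based on on-treatment data", meaning up to 1 day after the last dose.
- HBV DNA (SAP 8.1), including the all-B/F/TAF analysis: the same 1-day limit.
- Snapshot HIV-1 RNA (SAP 6.1.1.2): "All HIV-1 RNA data collected on-treatment (ie, data collected up to 1 day after permanent discontinuation of study drug) will be used".
- Full Analysis Set (SAP 3.1.1.2): all efficacy data of the randomized phase, "including data collected after the last dose of blinded study drug".

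**When samples are drawn off drug.** The procedures table (Protocol Appendix 2) schedules HIV-1 RNA at the 30-Day Follow-Up. Protocol 6.5.2 and 6.6.1 ask subjects who stop blinded drug to keep attending visits until the End of Blinded Treatment Visit. The notes to the virologic rebound schema (Protocol 6.11.1) allow a new ARV regimen while the subject remains in the study.

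**The concern.** A table labelled B/F/TAF should describe subjects while they take B/F/TAF, unless the plan says that it follows them regardless of treatment. As written, the percentage mixes samples taken on and after B/F/TAF, and no treatment-policy intent is stated. Because the last record in the window is selected, the off-drug sample does not merely join the on-drug one; it replaces it. Where the window holds no on-drug sample, the off-drug sample becomes the subject's only value for that visit.

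The bias can go either way. Rebound after stopping counts against B/F/TAF, and resuppression on another regimen counts for it. Some subjects may be taking B/F/TAF from another source at follow-up. The HIV-1 RNA and CD4 tables for the same analysis set would also rest on different data, so their visit denominators would not match in meaning.

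**Working it through.** **1. Reproduce the window.** SAP Table 3 gives Week K as Day (K−6)×7+1 to Day (K+6)×7. For K = 96: 90×7+1 = 631 and 102×7 = 714, as tabulated. In general the upper limit is Day 7K+42. From Week 24 onward each window is 84 days wide.

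**2. DTG+F/TAF-to-B/F/TAF subject, last dose at a scheduled open-label (OL) visit.**
- Study Day 1 is the first OL dose. Assuming it is taken on the day of the End of Blinded Treatment Visit, the Week K OL visit is Day 7K+1.
- Visit tolerance ±6 days (Protocol 6.5.3): Day 7K−5 to 7K+7, which is 13 possible days.
- Follow-up 30 ± 6 days after the last dose (Protocol 6.6.2): +24 to +36, which is 13 possible days.
- Follow-up therefore falls between 7K−5+24 = 7K+19 and 7K+7+36 = 7K+43.
- There are 13×13 = 169 combinations. Only the latest visit with the latest follow-up gives Day 7K+43, beyond the limit of 7K+42. So 168 of 169 fall in the same window.
- At Week 96 the range is Day 691 to 715 against an upper limit of Day 714.
- The result holds for every K from 12 to 96. If the visit is counted as Day 7K, all 169 fall inside (Week 96: Day 690 to 714).

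For OL discontinuers, Protocol 6.6.2 times the follow-up from the discontinuation visit, which may be up to 72 hours after stopping. Take a last dose at a scheduled visit and a discontinuation visit 3 days later. Write a for the visit deviation and c for the follow-up deviation, each from −6 to 6. The follow-up day is 7K+1+a+3+30+c, which stays in the window when a+c ≤ 8. Sums of 9, 10, 11 and 12 arise in 4+3+2+1 = 10 ways, leaving 159 of 169.

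**3. B/F/TAF-group subject who does not enter the OL phase.** Visits continue every 12 weeks, but the End of Blinded Treatment Visit is set by the timing of the Week 48 analysis, so it can fall anywhere in a window. Assume it is evenly spread over 84 days and coincides with the last dose. A follow-up d days later shares the window with probability (84−d)/84:

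| d (days) | Calculation | Same window |
|---|---|---|
| 24 | 60/84 | 71.4% |
| 30 | 54/84 | 64.3% |
| 36 | 48/84 | 57.1% |

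Otherwise the follow-up supplies the subject's only value in the next window.

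**4. Effect on a percentage.** Each value that changes category moves the visit percentage by 100/n points. For assumed n of 20, 100 and 280 this is 5.0, 1.0 and 0.36 points. The documents do not give the number of off-drug samples or how often the category changes.

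**5. With the CD4 limit applied.** A follow-up at 24 days or more after the last dose is always excluded by a 1-day limit, so the on-drug value stands.

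**The case against.** The strongest reply is that this is a deliberate convention: all efficacy data enter by default, and an on-treatment limit is added endpoint by endpoint. The Full Analysis Set definition has the same structure. The snapshot limit is also a weak comparator, because it belongs to an FDA-defined algorithm for a different endpoint. Both observations are fair. They show that the rule is stated, but not why HIV-1 RNA should be treated differently from CD4 and HBV DNA in the same analysis. The Full Analysis Set wording also confirms that the phrase about all efficacy data cannot be read as silently on-treatment.

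A second objection is that a 1-day cut brings its own bias. Discontinuation visits may fall up to 72 hours after stopping, and Protocol 6.11 counts HIV-1 RNA of 50 copies/mL or more at discontinuation as virologic failure. Under M=E, such samples drawn on days 2 to 3 would leave both numerator and denominator, which could flatter B/F/TAF. This stands, and the fix has to deal with it.

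Third, 168 of 169 counts equally weighted day combinations. It is not a share of subjects, and it applies only when dosing ends at a scheduled OL visit. Blinded-phase discontinuers, who can contribute several off-drug values, are not quantified. This also stands.

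Finally, the table is not a protocol primary or secondary endpoint, carries no between-group comparison and feeds no decision rule. That limits the consequence but does not remove the mixing.

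**Conclusion.** The concern holds. Followed as written, the plan reports post-treatment HIV-1 RNA under the B/F/TAF label and lets it replace on-drug values. Replacement is nearly certain for switched subjects whose dosing ends at a scheduled OL visit and who attend follow-up (168 of 169 combinations; 159 of 169 if follow-up is timed from a discontinuation visit 3 days later). For B/F/TAF-group subjects who do not enter the OL phase it is 57% to 71%, under the even-spread assumption. These figures describe where samples land, not how far the percentage shifts: the number of affected subjects, the rate of category change and the direction are unknown. The matter is confined to a descriptive table with Clopper-Pearson intervals and leaves the Week 48 snapshot endpoints untouched. It should be corrected before the final analysis, but it does not threaten the trial's main conclusion.

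**What to change.** In SAP 3.1.2.1 and 6.2.2.1, limit HIV-1 RNA in the M=E analysis to samples taken no later than 1 day after the last B/F/TAF dose, as 6.2.2.2 does for CD4. State that the limit is applied before the record selection in 3.8.3, and list later values.

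To cover the side effect, keep the all-data table as a labelled sensitivity analysis. Also list the subjects whose discontinuation-visit HIV-1 RNA is removed by the cut, with the value.

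If the sponsor does intend to include off-drug data, the SAP should say so, give the reason and label the table accordingly. That would make the table honest, but HIV-1 RNA and CD4 would still follow different rules.

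The cost is one sentence in each of two sections, one program filter, and one extra table or listing. Denominators become slightly smaller, and samples drawn 2 to 3 days after the last dose move to the sensitivity table and listing.

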# 3.2. Subject Grouping

For the randomized phase analyses using the All Randomized Analysis Set or the FAS, subjects will be grouped by the randomized treatment (labeled as B/F/TAF vs. DTG + F/TAF). For all other randomized phase analyses, subjects will be grouped by the actual treatment received. The actual treatment received will differ from the randomized treatment only when the actual treatment received differs from randomized treatment for the entire treatment duration.

For all B/F/TAF analyses, subjects will be grouped into the following 3 groups:

- B/F/TAF group: This group includes all subjects who actually received B/F/TAF in the randomized phase of this study, regardless whether subjects receive any B/F/TAF in the extension phase or not.
- DTG + F/TAF to B/F/TAF group: This group includes all subjects who actually received DTG + F/TAF regimen in the randomized phase of this study and then receive at least 1 dose of B/F/TAF in the extension phase
- All B/F/TAF group: This group includes all subjects who actually received at least 1 dose of B/F/TAF in either phase. This group includes the B/F/TAF group and the DTG + F/TAF to B/F/TAF group. Only data collected on and after the first dose date of B/F/TAF may be included.

Treatment comparisons will only be made between B/F/TAF and DTG + F/TAF for the randomized phase analysis.

